9.7 Follow-up of SAEs

If information is not available at the time of the first report becomes available at a later date, the investigator should complete a follow-up SAE form or provide other written documentation and fax it immediately within 24 h of receipt. Copies of any relevant data from the hospital notes (e.g., ECGs, laboratory tests, discharge summary, postmortem results) should be sent to the addressee, if requested.

Study No. CVN424-201 Page 53 of 73

Protocol v. 4.0 14 July 2021

All SAEs should be followed up until resuspension or permanent outcome of the event. The timelines and procedure for follow-up reports are the same as those for the initial report.

9.7.1 Safety Reporting to Investigators, IRBs or IECs, and Regulatory Authorities

The sponsor will be responsible for reporting all suspected unexpected serious adverse reactions (SUSARs) and any other applicable SAEs to regulatory authorities, including the European Medicines Agency (EMA), investigators and IRBs or IECs, as applicable, in accordance with national regulations in the countries where the study is conducted. Relative to the first awareness of the event by/or further provision to the sponsor or sponsor's designee, SUSARs will be submitted to the regulatory authorities as expedited report within 7 days for fatal and life-threatening events and 15 days for other serious events, unless otherwise required by national regulations. The sponsor will also prepare an expedited report for other safety issues where these might materially alter the current benefit-risk assessment of an investigational medicinal product or that would be sufficient to consider changes in the investigational medicinal products administration or in the overall conduct of the trial. The investigational site also will forward a copy of all expedited reports to his or her IRB or IEC in accordance with national regulations.

Study No. CVN424-201 Page 54 of 73

Protocol v. 4.0 14 July 2021

10.0 STUDY-SPECIFIC COMMITTEES

None.

(Review of incident and cumulative safety data and findings during study is the responsibility of the Medical Monitor and sponsor's Responsible Medical Officer.)

Study No. CVN424-201 Page 55 of 73

Protocol v. 4.0 14 July 2021

11.0 DATA HANDLING AND RECORDKEEPING

AEs, PTEs, medical history, and concurrent conditions will be coded using the Medical Dictionary for Regulatory Activities (MedDRA). Drugs will be coded using the World Health Organization Drug Dictionary. All terms will be coded using the dictionary version available at the start of the study.

11.1 CRFs (Electronic)

Completed eCRFs are required for each subject who signs an informed consent.

The sponsor or its designee will supply investigative sites with access to eCRFs. The sponsor will make arrangements to train appropriate site staff in the use of the eCRF. These forms are used to transmit the information collected in the performance of this study to the sponsor and regulatory authorities. eCRFs must be completed in English. Data are transcribed directly onto eCRFs.

After completion of the entry process, computer logic checks will be run to identify items, such as inconsistent dates, missing data, and questionable values. Queries may be issued by sponsor personnel (or designees) and will be answered by the site.

Corrections to eCRFs are recorded in an audit trail that captures the old information, the new information, identification of the person making the correction, the date the correction was made, and the reason for change. Reasons for significant corrections should additionally be included.

The Investigator must review the eCRFs for completeness and accuracy and must sign and date the appropriate eCRFs as indicated. Furthermore, the investigator must retain full responsibility for the accuracy and authenticity of all data entered on the eCRFs.

eCRFs will be reviewed for completeness and acceptability at the study site during periodic visits by study monitors. The sponsor or its designee will be permitted to review the subject's medical and hospital records pertinent to the study to ensure accuracy of the eCRFs. The completed eCRFs are the sole property of the sponsor and should not be made available in any form to third parties, except for authorized representatives of appropriate governmental health or regulatory authorities, without written permission of the sponsor.

11.2 Record Retention

The investigator agrees to keep the records stipulated in Section 12.1 and those documents that include (but are not limited to) the study-specific documents, the identification log of all participating subjects, medical records, temporary media such as thermal sensitive paper, source worksheets, all original signed and dated ICFs, subject authorization forms regarding the use of personal health information (if separate from the ICFs), copy of eCRFs, including the audit trail, and detailed records of drug disposition to enable evaluations or audits from regulatory authorities, the sponsor or its designees. Any source documentation printed on degradable thermal sensitive paper should be photocopied by the site and filed with the original in the subject's chart to ensure long-term legibility. Furthermore, ICH E6 Section 4.9.5 requires the investigator to retain essential documents specified in ICH E6 (Section 8) until at least 2 years after the last approval of a marketing application for a specified drug indication being investigated or, if an application is not approved,

Study No. CVN424-201 Page 56 of 73

Protocol v. 4.0 14 July 2021

until at least 2 years after the investigation is discontinued and regulatory authorities are notified. In addition, ICH E6 Section 4.9.5 states that the study records should be retained until an amount of time specified by applicable regulatory requirements or for a time specified in the Clinical Study Site Agreement between the investigator and sponsor.

Refer to the Phase 1 Site Specifications document for the sponsor's requirements on record retention. The investigator should contact and receive written approval from the sponsor before disposing of any such documents.

Study No. CVN424-201 Page 57 of 73

Protocol v. 4.0 14 July 2021

12.0 STATISTICAL METHODS

12.1 Statistical and Analytical Plans

A statistical analysis plan (SAP) will be prepared and finalized prior to unblinding of subjects' treatment assignment. This document will provide further details regarding the definition of analysis sets, analysis variables and analysis methodology to address all study objectives.

A targeted data review will be conducted prior to unblinding of subjects' treatment assignment. This review will assess the accuracy and completeness of the study database, subject evaluability, and appropriateness of the planned statistical methods.

12.1.1 Analysis Sets

Safety Set

The Safety Analysis Set will consist of all subjects who enrolled and received at least 1 dose of study drug, classified according to the treatment they actually received. Subjects in this analysis set will be used for demographic, baseline characteristics and safety summaries.

Efficacy Set

The primary Efficacy Analysis set will consist of all subjects who were eligible, randomized, and received at least one dose of study drug, classified according to the treatment actually received. Secondary tests of efficacy will assess subjects who were eligible, randomized, and judged compliant with treatment and follow-up as classified prior to breaking the blind. The former is less stringent than a formal intent-to-treatment sample but estimates the efficacy one might expect among subjects who start using CVN424 at a specified dose, acknowledging that some will be intolerant or non-compliant. The latter estimates the maximal efficacy, the efficacy one might expect among subjects who are tolerant of and compliant with treatment. Subjects in this analysis set will be used for efficacy analyses.

PK Set

The PK set will consist of all subjects who received at least 1 dose of study drug and have at least 1 measurable plasma concentration. Subjects in this analysis set will be used for analysis of pharmacodynamics.

If any subjects are found to be noncompliant in dosing schedule or with incomplete data, a decision will be made on a case-by-case basis as to their inclusion in the analysis prior to breaking the blind, but they will be presented in the subject listings.

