Efficacy will be assessed among all subjects who were eligible, randomized, and received at least one dose of study drug, classified according to the treatment actually received. Secondary tests of efficacy will assess subjects who were eligible, randomized, and judged compliant with treatment and follow-up as classified prior to breaking the blind. Serial assessments of average daily hours of OFF time as recorded in the Patient Motor Diary over the two days prior to each visit will be using mixed model for repeated measures (MMRM). The model will include fixed terms for treatment, visit, treatment x visit interaction and baseline measurement with subject-level unstructured covariance among repeated measurements. Other covariance structures may be used in case the model do not converge using unstructured covariance structure. Additional covariates may be included based on review prior to breaking the blind. The primary estimand of efficacy for each active dose vs. placebo will be the treatment-dependent difference in change from baseline to Day 27 and will be tested using linear contrasts of least-square means. Each comparison will test for significance at one-tailed p < 0.1 to control the overall type 1 error rate at 20% based on Dunnett's method for comparing two treatments to the same control. Additional contrasts will be used to test for a dose-dependent effect of treatment and to estimate dosage-dependent differences in change from baseline at all other visits. Additional and exploratory efficacy endpoints will be analyzed in the same model and using the same estimands. Subgroup analyses will assess the influence of selected demographic and disease-related characteristics.

PK Measures:

Concentrations of CVN424 in plasma will be summarized by dose level and by gender (if possible) over each scheduled sampling time using descriptive statistics. Individual plasma concentration data versus time will be presented in a data listing. PK parameters of CVN424 will be summarized by dose and by gender (if possible) using descriptive statistics.

Sample Size Justification:

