A first-in-humans safety study of CVN424 in 64 healthy volunteers has been completed (NCT03657030); the study findings are summarized in the Investigator's Brochure. In brief, CVN424 was safe and well tolerated when administered to healthy subjects as a single oral dose of between 1 mg and 225 mg, or when administered as 7 daily oral doses of between 25 mg and 150 mg. Study drug-related adverse events (AEs) were reported by 2 of 40 subjects (5.0%) overall in the single-dose cohorts (feeling hot; headache). Study drug-related AEs were reported by 2 of 24 subjects (8.3%) overall in the multiple-dose cohorts (dysphagia; chills). With one exception, all AEs were mild in severity; dysphagia of moderate severity led to treatment discontinuation in one subject after their third daily dose (75 mg). There were no severe or serious AEs, and all AEs had resolved by the end of the study. Administration of the first dose of CVN424 was associated with an elevation in group mean and median body temperature. These changes were detectable at 1 h post-dose (the earliest scheduled post-dose assessment), increased further by 6 h post-dose, and spontaneously returned to baseline by 24 h post-dose. The increases tended to be larger at higher doses but did not appear to be strictly dose-proportional. A trend of increase in heart rate while standing was also observed with a similar time course and relationship to dosage. These trends were not considered clinically significant, and no individual vital sign measurement was reported as an AE. In the multiple-dose cohorts, elevations in body temperature and heart rate were observed only after the first dose of CVN424, not following subsequent doses. No other trends in vital sign measurements

Study No. CVN424-201 Page 19 of 73

Protocol v. 4.0 14 July 2021

were noted. No treatment-related trends were observed in the clinical laboratory results or 12-lead electrocardiogram (ECG) measurements.

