12.1.5 Efficacy Analysis

Serial assessments of average daily hours of OFF time as recorded in the Patient Motor Diary over the two days prior to each visit will be analyzed using mixed model for repeated measures (MMRM). The model will include fixed terms for treatment, visit, treatment x visit interaction and baseline measurement with subject-level unstructured covariance among repeated measurements. Other covariance structures may be used in case the model does not converge using unstructured

Study No. CVN424-201 Page 60 of 73

Protocol v. 4.0 14 July 2021

covariance structure. Additional covariates may be included based on review prior to breaking the blind. Two co-primary estimands of efficacy will estimate treatment-dependent difference in change from baseline to Day 27, one for each active dose vs. placebo, and will be tested using linear contrasts of least-square means. Each co-primary comparison will test for significance at one-tailed p < 0.1 to control the overall type 1 error rate at 20% based on Dunnett's method for comparing two treatments to the same control. Additional contrasts will be used to test for a dose-dependent effect of treatment and to estimate dosage-dependent differences in change from baseline at all other visits. Additional and exploratory efficacy endpoints will be analyzed in the same model and using the same estimands.

Responder analysis will ascertain the incidence of clinically significant improvement.

Subgroup analyses will ascertain the potential impact on efficacy of subgroup variables reflecting various demographic and disease-related characteristics.

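### The compliant-subset efficacy comparison is not protected by randomisation, so it estimates neither a maximal effect nor the effect in patients tolerant of CVN424

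*Combined protocol and SAP*

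**What the plan says.** Section 12.1.1 (Analysis Sets) defines two efficacy sets. The primary one holds eligible, randomised subjects who took at least one dose, "classified according to the treatment actually received". For the other it says: "Secondary tests of efficacy will assess subjects who were eligible, randomized, and judged compliant with treatment and follow-up as classified prior to breaking the blind". This definition is repeated in the Study Summary (Section 2.0, Efficacy).

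Section 12.1.1 then interprets each set. The all-treated set is said to show what to expect in people who start CVN424, "acknowledging that some will be intolerant or non-compliant". Of the compliant set it says: "The latter estimates the maximal efficacy, the efficacy one might expect among subjects who are tolerant of and compliant with treatment".

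The text gives no compliance threshold, no adjustment for selection and no sensitivity analysis for the compliant set. At the end of the same section stands the rule "If any subjects are found to be noncompliant in dosing schedule or with incomplete data, a decision will be made on a case-by-case basis", to be applied before the blind is broken. It follows the PK set, so whether it also governs the efficacy sets is unclear. Section 12.1 leaves further definition of analysis sets to a SAP, whose details are not in the text reviewed.

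**The concern.** The compliant set is applied to every arm. On CVN424 it keeps those who tolerated and took CVN424; on placebo it keeps those who tolerated and took placebo. A placebo subject who would not have tolerated CVN424 stays in, and nobody can identify that subject. The two retained groups may therefore differ in prognosis even though the randomised groups did not. Requiring compliance with follow-up adds selection on having the outcome recorded.

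The sentence in Section 12.1.1 gives the result a property that the design does not supply. Without a further assumption, which the protocol does not state, the contrast is not the effect in patients tolerant of CVN424. Since the bias can have either sign, it is not a maximum either. A reader who takes the label at face value could carry the figure forward as the effect of CVN424 when taken as directed.

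**Working it through.** **Inputs from the documents.** SD 3 h for change in OFF time, 45 per arm, 20% non-evaluable, target 1.5 h, 80% power (Section 12.3); one-tailed p < 0.1 per comparison (Section 12.1.5), critical value 1.282.

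**The plan's own figure.** 45 × 0.8 = 36 evaluable per arm. SE = 3 × √(2/36) = 0.707 h. Power = Φ(1.5/0.707 − 1.282) = Φ(0.840) = 79.9%, against a stated 80%. The inputs are therefore read as the plan intends. This power figure does not depend on the point at issue.

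**Illustration of the bias, with zero true effect.** Assumptions, not document figures: a share p of an arm is excluded for poor tolerance, and tolerance correlates ρ with change in OFF time, so that those excluded would have done worse. The retained mean in an arm then shifts by −ρ × SD × λ(p), where λ(p) = φ(z)/(1 − p) and z is the upper-p normal quantile.

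- λ(0.05) = 0.1031/0.95 = 0.109
- λ(0.10) = 0.1755/0.90 = 0.195
- λ(0.15) = 0.2332/0.85 = 0.274
- λ(0.20) = 0.2800/0.80 = 0.350

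Spurious benefit b = ρ × 3 × [λ(drug) − λ(placebo)]. SE = 3 × √(1/[45(1 − p_drug)] + 1/[45(1 − p_placebo)]). False-positive rate = Φ(b/SE − 1.282). SD is held at 3 h after selection, a small approximation.

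| Excluded, drug vs placebo | ρ | b (h) | SE (h) | False positives |
|---|---|---|---|---|
| 10% vs 5% | 0.1 | 0.03 | 0.658 | 10.7% |
| 10% vs 5% | 0.3 | 0.08 | 0.658 | 12.2% |
| 10% vs 5% | 0.5 | 0.13 | 0.658 | 13.9% |
| 15% vs 5% | 0.3 | 0.15 | 0.668 | 14.5% |
| 15% vs 5% | 0.5 | 0.25 | 0.668 | 18.2% |
| 20% vs 5% | 0.3 | 0.22 | 0.679 | 16.8% |
| 20% vs 5% | 0.5 | 0.36 | 0.679 | 22.7% |

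Against the 1.5 h target, 0.03 h is about 2% and 0.36 h about 24%.

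**Reversed sign.** If those excluded would have done better (ρ = −0.5, 20% vs 5%), b = −0.36 h. The chance of declaring benefit falls to Φ(−0.534 − 1.282) = 3.5%, and the set understates the drug.

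**Second method.** Let q0 and q1 be the non-compliant shares on placebo and drug, and let the extra drug-arm non-compliers be g hours worse than the rest. Then b = (q1 − q0)/(1 − q0) × g. With 10%, 20% and 1.5 h: 0.10/0.90 × 1.5 = 0.17 h, SE = 3 × √(1/40.5 + 1/36) = 0.687 h, false positives Φ(0.243 − 1.282) = 15%. This agrees in order of size. An extreme choice (5%, 30%, 3 h) gives 0.79 h and 44%, but nothing in the documents points there.

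**Equal exclusion rates do not protect.** Exclude 20% from each arm. If placebo non-compliers run 1.5 h worse than their arm's mean and drug non-compliers 1.5 h better, each arm's compliers shift by 0.2 × 1.5/0.8 = 0.375 h in opposite directions, a spurious 0.75 h benefit. Swapping the two gives −0.75 h.

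**The case against.** **The sentence defines its own term.** It explains maximal efficacy as efficacy among tolerant, compliant subjects, in contrast to the all-treated set, and claims no formal upper bound. That is fair, and a reader should not infer that the protocol asserts one. But the definition it gives instead, efficacy in patients tolerant of treatment, is also not what the contrast delivers.

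**Treatment-dependent compliance is not shown.** This stands. Section 4.1 reports one treatment discontinuation (dysphagia, 75 mg) among 24 multiple-dose volunteers, and first-dose temperature and heart-rate rises that were not considered clinically significant. Section 6.1 steps up the high dose to limit those changes. With the expectation of intolerance in Section 12.1.1, this makes dependence plausible but does not establish it. If the same subjects would comply on either arm, the comparison would be unbiased for that subgroup.

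**The illustration rests on chosen inputs.** This stands too. The 20% in Section 12.3 is overall non-evaluability and not an excess on drug. A gap of 8% versus 5% at correlation 0.3 gives only 0.05 h and 11%. It would be tempting to infer that the set must favour CVN424; the sign reversal shows that this does not follow.

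**The set is secondary.** It is classified blind, reported beside an analysis that keeps non-compliers, and belongs to a phase 2 trial whose primary endpoint is safety. All this limits the consequence. Blinded classification does stop analysts choosing subjects by arm, but it does not make compliance independent of arm.

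**A separate on-treatment analysis is the natural remedy.** It would add little. Appendix A schedules post-baseline diaries only at Days 15 and 27, with none at Day 35 or Early Termination. Few diaries after stopping drug would exist to set aside, and the rerun would nearly repeat the planned mixed model.

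**Conclusion.** The point holds as one of interpretation and labelling. The compliant-subset contrast is a non-randomised comparison, and the property that Section 12.1.1 gives it does not follow from the design. In the tabulated scenarios the spurious benefit under no effect is 0.03 to 0.36 h, with false-positive rates of 10.7% to 23% against a nominal 10%. The opposite sign is equally possible. These figures depend on assumed exclusion rates and correlations, and the bias is modest when non-compliance is low.

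Three stronger readings are not supported: that compliance in this trial does depend on treatment, that the bias must favour CVN424, and that the all-treated efficacy analysis is compromised by this point. The all-treated set is itself not a strict intention-to-treat set, as Section 12.1.1 acknowledges, but it keeps subjects who later prove intolerant or non-compliant.

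**What to change.** In Section 12.1.1, and in the SAP wherever the set is described, replace the sentence on maximal efficacy with a statement that:

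- the compliant-subset result is supportive only;
- it is a non-randomised comparison that may over- or understate the effect;
- it will not be used alone to claim efficacy, nor serve as the effect estimate.

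Beside it, report the number of subjects excluded and the reasons, by arm. Base efficacy conclusions on the all-treated mixed model. No extra on-treatment model is needed, and a significance test in the subset need not be banned once it is labelled this way.

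The cost is a wording change before unblinding and one table. The downside for the sponsor is the loss of a potentially favourable headline figure.

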12.1.2 Analysis of Demographics and Other Baseline Characteristics

Descriptive statistics (N, mean, SD [standard deviation], median, minimum, and maximum) will be generated for continuous demographic variables and baseline characteristics variables (age, height, weight, and BMI) for placebo, each CVN424 dose level, CVN424 overall, and overall. The number and percentage of subjects in each class of the categorical demographic variables and baseline characteristics variables (gender, ethnicity, and race) will be tabulated for placebo, each CVN424

Study No. CVN424-201 Page 58 of 73

Protocol v. 4.0 14 July 2021

dose level, CVN424 overall, and overall. Individual subject demographic and baseline characteristics data will be listed.

Demographic variables of screen failure subjects and reasons for screen failures will be summarized overall for subjects who are screened, but not enrolled in the study. Individual demographic characteristics, date of informed consent, and reason for screen failure will be listed.

